## 6.2 Smartphone Assessments

The following motor activities will be completed by the participant:

- Gait Task - A 30 second walking task where the participant will walk with their phone in their pocket to measure gait using the phone accelerometer and gyroscope.
- Finger Tapping Task - A 30 second speeded tapping task in each hand where screen presses are captured.
- Resting Tremor Task - A 30 second task in each hand where the participants hold the phone with their hand in their lap while the phone records accelerometer and gyroscope readings.

- Balance task - A standing task where the participant tries to stand still while the phone measures accelerometer and gyroscope readings.

The participant will be asked to complete cognitive tasks, which may include the following:

- Digit Span - A short term memory test in which the participant reports back a series of numbers that were displayed rapidly to them.
- Digit Symbol Substitution Tests - A neuropsychological test sensitive to brain damage, dementia, age and depression. It consists of (e.g. nine) digit-symbol pairs followed by a list of digits. Under each digit the subject should write down the corresponding symbol as fast as possible.
- Spatial Working Memory - A neuropsychological test that tests memory and manipulation visuospatial information.

### 6.3 Fox Insight (FI) Assessments

FI is a separate online research study with a separate consent process. As such, the assessments will not be described in detail. The following validated assessments are included in FI:

- The Parkinson's Disease Questionnaire, short-form 8 item version (PDQ-8)
- MDS-UPDRS part 2
- Physical Activity Scale for the Elderly (PASE)
- Your Cognition and Daily Activities (PDAQ-15)
- Euroqol Five (EQ-5D)
- Non-motor symptoms questionnaire (NMS-QUEST)
- Geriatric Depression Scale, short form (GDS)
- Parkinson's disease-Patient Reported Outcomes of Problems (PD-PROP)

The complete list of assessments can be found in the SOA. Participants are also invited to complete additional PRO surveys about, but not limited to, symptoms, disease progression, quality of life, patient preference and general health.

### 6.4 Safety Assessments (see Section 9 Reportable Events)

As this is a minimal risk observational study that does not involve a drug or device intervention, adverse events are not anticipated and will not be assessed. Safety assessments will be limited to the collection of reportable events either spontaneously offered by the participant or observed by a study team member during a tele-visit.

### 6.5 Assessment of Participant Compliance

At each tele-visit, the Investigator and/or study team member will assess the participant's compliance with the study requirements. This

will include checks of protocol compliance, including completion of surveys for tele-visits, smartphone tasks (where applicable), and FI survey completion (where applicable). More detail regarding the monitoring of compliance can be found in Section 5.5.

While we will strive to retain all participants, we will consider successful participants to be those who complete at least six of nine smartphone-based test batteries over 24 months- including two of the three sets that coincide with the tele-visits.

## 7. COSTS TO THE SUBJECT

There is no direct cost to the participants to participate in this study. If they participate in the smartphone component of this study, data collected through the app may count against their existing mobile data plan. The internet connection can be configured within the app to only use Wi-Fi connections to limit the impact running this app has on the data costs. Subjects will not have to pay for research procedures.

## 8. PAYMENT FOR PARTICIPATION

Participants will be compensated \$50 for each tele-visit completed, as applicable (baseline, month 12 and month 24) for a total of up to \$150 for expenses incurred to participate in the AHPD study via a check. They will not be paid for tele-visits that they do not complete. If a web camera is provided to the participants, they will be allowed to keep it after completion of the study for their own use.

The costs of standard internet access and/or a smartphone/data plan (above the compensation amount) will be reimbursed for minority participants currently enrolled in STEADY-PD III or SURE-PD3 who are interested and otherwise eligible to enroll but do not have the requisite technical resources.

## 9. RISK/BENEFIT ASSESSMENT

### 9.1 Potential Risks

The risks of participating in this study are very low.

- The most common risk is discomfort with some of the questions or assessments.
- Some of the questions in the questionnaires may be upsetting or make the participant feel uncomfortable. They may feel frustrated while taking a test used to evaluate the memory or thinking: it is meant to be challenging.
- During the tele-visits the study team will watch the participant walk, and there is a possibility that they could fall.
- Another risk is breach of confidentiality if someone were to access the study information without authorization. Because this study involves collecting personal, identifiable information, there is a potential for invasion of privacy or breach in confidentiality. Accidental release of information to the public may occur due to

unintended data breaches. In such an event, that the data may be misused or used for unauthorized purposes.

#### Smartphone Application

There are a few additional risks to participating in the smartphone assessments:

- Other people may glimpse the study notifications and/or reminders on the smartphone and may become privy to the information that the participant is enrolled in this study. This can make some people feel self-conscious.
- There is a potential for invasion of privacy or breach of confidentiality. The data collected through the mPower app will be encrypted on the smartphone, transferred electronically and stored securely in Synapse. Sage team will separate the participant account information (name, email, contact information, etc.) from the study.
- Sage will not access the personal contacts, other apps, text or email message content, or websites visited.

## 9.2 Protection Against Risks

- Participants are free to stop a test at any time. Participants can take breaks as needed.
- If they typically walk with an assistive device (such as a cane or walker) or with the help of a caregiver, they will only be asked to walk under their usual conditions. Participants will not be asked to try to walk if they typically use a wheelchair or if they or the investigator has concerns about the risk of falling. If a participant does fall during the visit, or have another medical event during the tele-visit that requires emergent evaluation, the study investigator or a team member will assist in contacting emergency services if needed.
- Every effort will be made to maintain confidentiality and protect personal information obtained as a result of this study.
- Study team will assign a GUID number instead of labeling the information collected from the participant with their name (or medical record number). Study team will use GUID instead of the name on all the study data. Information about the GUID number will be kept in a secure system. Only the study investigators and some technical staff for AHPD, STEADY-PD III or SURE-PD3 studies and some FI clinical operations staff will have the key to link the coded study data to the participant name and account information.
- Study will use a HIPAA compliant, secure video-conferencing system for the tele-visits. Note: real time video conferencing will be used to complete the assessments which will not be recorded.
- The software that will be used for the surveys and to store the information from the tele-visits has been specifically designed to protect the privacy of research subjects and access to the database is restricted.

- Data obtained through Fox Insight questionnaires are stored in a secure databank. Only the Fox Insight study team will have access to this information before any parts that could identify the participants will be removed.
- The study combined data will be stored securely in Sage Bionetworks' databank Synapse (synapse.org), using Amazon-Web Cloud Services.

### 9.3 Potential Benefits to Subjects

Participants will not benefit directly from being in this research study. Benefits may include contributing to the future research advances and experiencing new ways of tracking and measuring the disease.

### 9.4 Alternatives to Participation

If the participant elects not to participate in the study, there are no alternatives available.

## 10. CONCOMITANT MEDICATIONS

### 10.1 Required Therapy

There is no restriction on medications in this study. All concomitant medications will be recorded.

## 11. PARTICIPANT WITHDRAWALS/DROPOUTS

Participants will be advised in the written informed consent forms that they have the right to withdraw from the study at any time without prejudice and may be withdrawn at the Investigator's or sponsor's discretion at any time.

Premature withdrawal will be defined as withdrawal from the tele-visit component (or the full study) prior to completion of the month 24 tele-visit. If a participant who has started the study terminates the study prematurely, every effort should be made to complete the premature withdrawal visit. Reasonable effort should be made to contact any participant lost to follow-up during the course of the study in order to complete study related assessments and retrieve any outstanding data. Participants may be deemed lost to follow-up after 15 months without contact. Contact attempts may include phone calls, emails, and physical mail. Such efforts should be documented in the source documents.

A participant may withdraw or be withdrawn from the study for the following reasons:

- Administrative
  1. Withdrawal of consent
  2. Participant deemed lost to follow-up
  3. Premature withdrawal of study

- Medical Events
  1. Death
  2. Other reportable event that precludes further study participation

***Participant premature withdrawal should be reported to the CTCC Project Manager within 5 business days of site's knowledge of the event.***

The Demographic form must be completed for all study participants who provide informed consent. This includes participants who completed the study or withdrew/were withdrawn from the study or were screened and provided consent but did not start the study.

The Conclusion of Study Participation form should be completed for all participants who have been enrolled. If a participant withdraws due to a reportable event, the site must ensure that the event is captured on the reportable event form.

## 12. REPORTABLE EVENTS

Based on the nature of the study, routine adverse events will not be collected. In this study, the following pre-specified events that are thought to be relevant to the safety and feasibility of the study population will be considered Reportable Events (RE). REs will be assessed at the tele-visits and reported on the RE log within 72 hours of the event, or the CHeT Site Investigator's knowledge of the event.

- Compromise of confidentiality
- Loss of competence to consent
- Withdrawal from the study
- Severe depression and suicidal ideation
- Suicide attempt
- Hospitalization for serious (non-elective) medical issues (including childbirth)
- Any psychiatric hospitalization
- Participant intends to or has participated in another research study involving experimental interventions
- Any neurologic event (e.g., TBI, Seizure, etc.)
- Identification of a safety concern warranting referral for medical evaluation
- Identification of a safety concern warranting referral for psychiatric evaluation
- Death

Although not a reportable event the enactment of the Medical Safety Escalation Plan should be reported to the CTCC PM

Enactment of the Medical Safety Escalation Plan (see section 9.2)

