The CGIS is rated on a 7-point scale, with the severity of illness scale using a range of responses from 1 (normal) through to 7 (amongst the most severely ill patients). CGIC scores range from 1 (very much improved) to 7 (very much worse).

Similarly, the PGI is a patient-rated scale that measures illness severity (PGIS) and global improvement of change (PGIC).

g. Falls Assessment

Falls will be assessed using two questionnaires, which have been incorporated into an on-going large prospective study (PPMI). The self-reported falls assessment is a 1-item questionnaire that will be completed by the participant. The determination of falls assessment, which will be completed by the investigator, includes questions about freezing of gait and falls over two time periods (the past week and the past 12 months).

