We will compare TV vs. calibrated SP measures of disease progression generally, as predictors of future clinical events and changes in patient reported outcomes, and between specific subsets of participants expected to progress at different rates (Aim 2b) due to biology or treatment. After calibration, we will estimate the standard error for a treatment-group comparison from a two-arm trial using measure-specific variance components from a bivariate random-slopes linear mixed model for each pair of TV and SP measures and assuming an assessment schedule appropriate for each measure, e.g., annual for TV measures and quarterly for SP measures. Preferred measures would have smaller standard errors, and specifically, the ratio of squared standard errors provides an estimate of the relative sample size required. We will use the same approach to identify measures that are significantly more sensitive to biological

subgroups (e.g., among participants stratified by their rate of MDS-UPDRS progression over the first 2 years of in-clinic follow-up in the parent trials) or treatment-based subgroups (e.g., participants randomized to Isradipine or serum urate elevation). To compare TV assessments and SP measures with respect to their accuracy in predicting future clinical events and changes in patient reported outcomes, we will use the same 2:1 training: validation split and train separate models using TV and SP metrics collected over the first year of follow-up to predict clinical events and changes in PROs over the second year of follow-up. Clinical events will include dropping below 80% on the modified Schwab and England ADL and experiencing a fall. PROs of interest will include summary scores from the PDQ-8, EQ-5D, and PDAQ-15 and measures derived from the PD-PROP. Selection of the best training models will be based on 10-fold cross-validated accuracy for binary outcomes and residual sum of squares for continuous measures. Positive and negative predictive values of TV and SP-derived predictions will be estimated from the validation sample for binary outcomes and compared by logistic regression. For continuous outcomes, RSS estimates will be compared between TV and SP-derived predictions. As an exploratory analysis, additional models that combine TV and SP measures will be constructed and tested for accuracy relative to models derived from TV or SP measures alone.

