### 13.6 Safety Analysis

RE information collected at study tele-visits will be summarized. All participants will be included in the safety analysis. At a minimum, individual report information will be displayed, and RE rates tabulated.

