## 17. SAFETY MONITORING

All aspects of the study will be monitored by the CHeT Site Investigator and designees in compliance with Good Clinical Practice (GCP) and applicable regulations. There is no clinical monitor or safety monitoring committee for this study. The Steering Committee will review collected reportable events on a quarterly basis.

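### A fall during a study procedure is not a named Reportable Event, so only falls that also meet another category reach the safety summary and the Steering Committee, and no procedure-related fall rate can be tabulated

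*Combined protocol and SAP*

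**What the plan says.** Section 9.1 states: "During the tele-visits the study team will watch the participant walk, and there is a possibility that they could fall". Its other entries concern discomfort, frustration and confidentiality, and the additional smartphone risks concern privacy only. Section 9.2 limits walking where there is concern about falling and offers help in contacting emergency services, but gives no step for recording a fall.

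On collection, Section 6.4 says that "adverse events are not anticipated and will not be assessed" and restricts safety data to REs that are volunteered, or seen by staff, at a tele-visit. Section 12 lists 12 REs, none of which names a fall or procedure injury, and adds: "Although not a reportable event the enactment of the Medical Safety Escalation Plan should be reported to the CTCC PM". Section 12.1 requires the RE log to hold a description of each event and the investigator's view of its relatedness to the study.

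On analysis and oversight, Section 13.6 says "RE information collected at study tele-visits will be summarized", with individual reports and RE rates as the minimum output. Section 17 says "The Steering Committee will review collected reportable events on a quarterly basis" and that there is no clinical monitor or safety monitoring committee.

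Falls are also gathered as an outcome. A one-item self-report covers the last month (appendix surveys), and the investigator form in Section 6.1 g "includes questions about freezing of gait and falls over two time periods (the past week and the past 12 months"). Section 13.2 uses falls under Aim 2b: "Clinical events will include dropping below 80% on the modified Schwab and England ADL and experiencing a fall". Section 6.2 describes the gait task as "A 30 second walking task where the participant will walk with their phone in their pocket", and the balance task as standing still.

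**The concern.** Section 12 says its events were chosen as relevant to safety and feasibility. The one physical harm the risk section foresees is not among them, and no general adverse event collection stands behind the list.

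The study sets out to pilot a fully virtual model for long-term follow-up and to inform future Parkinson's disease trials. Whether people fall while doing the remote examination or the phone tasks is a basic question about such a model. As written, a report of few or no procedure-related falls could not be interpreted, because falls without a listed consequence are never counted.

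**Working it through.** No alpha, power or effect estimate is involved. The check sets the sections side by side and adds one exposure calculation.

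1. **Named risk against the RE list.** Of the 12 categories in Section 12, 0 name a fall or procedure injury. At least 4 can capture a fall through its consequence: a neurologic event (traumatic brain injury is an example given), a non-elective hospitalization, a safety concern that leads to medical referral, and death.

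2. **Tracing two falls.**
   - A fall at a tele-visit that causes a head injury is an RE as a neurologic event. It is logged with description and relatedness (12.1), displayed in 13.6 and reviewed quarterly (17).
   - A fall during a gait task at home, with an injury treated without admission or study referral, matches none of the 12. It appears neither in 13.6 nor in the quarterly review.

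3. **Whether the falls questionnaires fill the gap.** They cover the past week, the last month and the past 12 months. The documents do not tie them to study tasks or to 13.6. The SUPER-PD sub-study (about 50 participants, one tele-visit each including MDS-UPDRS part 3) has no falls form in its schedule, Table 3.

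4. **Exposure to the smartphone tasks.** Inputs: about 340 smartphone participants (Section 4.1.1), 9 sessions (Section 5.5 d), 10 motor sets per session (Schedule of Activities), and one complete set at each of 3 tele-visits.
   - Scheduled motor sets at full compliance: 340 x 9 x 10 = 30,600, each with a gait and a balance task.
   - Sets within tele-visits: 340 x 3 = 1,020.
   - Share within tele-visits: 1,020 / 30,600 = 3.3%, so about 97% are outside.
   - At the 6-of-9 success level in Section 6.5: 340 x 6 x 10 = 20,400 sets. With the required two coinciding with tele-visits, 340 x 2 = 680, and 680 / 20,400 = 3.3%. With all three, 1,020 / 20,400 = 5.0%. Between 95% and 97% are therefore outside tele-visits.

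   Dropout lowers these totals. Sets done beyond the 10-per-session minimum raise them.

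5. **Exposure to tele-visits.** 420 x 3 = 1,260 in the main study, plus about 50 in the sub-study, gives about 1,310 before dropout.

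6. **How a home fall would surface.** Section 12 has REs assessed at tele-visits, which are annual, and Section 6.4 relies on what participants volunteer or staff observe. A fall during an unsupervised task thus depends on unprompted recall, and it would be logged only if it met one of the existing categories.

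**The case against.** The strongest reply is that this is a minimal-risk observational study that deliberately collects consequential events only. A fall with serious consequences is an RE already. Its log entry would show that it was a fall and whether the study caused it, and 13.6 displays individual reports. That stands. A reader might infer that the safety summary and the committee would miss this harm altogether, and the documents do not support that. The gap is limited to falls that meet no other category, and to the lack of a category from which to compute a rate.

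A reader might also infer that keeping plan enactment off the RE list hides emergencies. It does not: enactment is an action, and the event that triggered it can still be an RE, for example through the referral category. Section 12.2 says the plan also covers non-urgent situations, so enactment is not itself a harm. The document history shows that the exclusion was a deliberate change in version 2.0, with a report to the project manager kept.

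Third, it is tempting to call the cohort prone to falls because Section 1.1 has participants nearing the stage when postural instability appears. The same passage says follow-up may be too short to see it emerge.

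Section 9.2 limits walking where falling is a concern, the remote motor examination omits postural instability testing, and Section 17.3 keeps calls about possible adverse events in source records. These reduce risk or leave a trace, but they do not produce a count. Section 13 defers detail to a separate SAP that takes precedence and is not in the combined document, and the investigator falls form is not in the appendix. Either might add something, but an analysis plan cannot tabulate falls that were never logged as such.

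**Conclusion.** The point holds in this form. A fall during a study procedure, the only physical injury risk that 9.1 names, reaches 13.6 and the Steering Committee only by also meeting another RE category, and its rate cannot be tabulated. The unsupervised phone tasks carry the same gap over 30,600 scheduled motor sets at full compliance, 95% to 97% of them outside tele-visits depending on compliance, and 9.1 lists no physical risk for them.

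The exposure figures rest on the plan's projected enrolment and schedule. The documents give no fall rate and no share of falls that would meet another category, so the number of missed falls cannot be stated. This is a cheap improvement to a design choice. It is not an error that threatens the study's main analyses.

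**What to change.** 1. Add one category to the Section 12 list, for the main study and the SUPER-PD sub-study: *Fall during a study procedure (tele-visit examination or smartphone gait/balance task)*.
2. Ask about it directly when REs are reviewed at each tele-visit. Leave the falls questionnaires unchanged, since they are shared with another large prospective study (PPMI).
3. In 13.6, give it its own row: participants, events, events per tele-visit, and events per completed motor set. Smartphone data are already deposited in Synapse daily, so the denominator is available.
4. Add the fall risk to the smartphone risks in 9.1, and align 6.4.
5. Plan enactment can stay outside the RE list as the sponsor chose. A count of enactments for the Steering Committee is optional.
6. Reconcile two cross-references: Section 12 points to 9.2 for the escalation plan, which is described in 12.2, and the heading of 6.4 points to Section 9 for REs, which are in Section 12.

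The cost is a short amendment, one log category, one question and one table row, with no extra staff and no change to clinical handling. The downsides are a few more log entries and reliance on recall over about a year for falls during phone tasks, so that rate should be read as a lower bound. Falls unrelated to study tasks would gain no RE category of their own.
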